3.0 STUDY DESIGN

TREATMENT PHASE

This study will employ an open label nonrandomized design in the treatment of subjects with JDM. Study participation will consist of a screening visit and 5 protocol visits over six months (week 0, week 6, week 12, week 18, and week 24) for each subject, and phone follow-up in between in-person visits (week 2, week 4, week 8, week 10, week 14, week 16, week 20, and week 22). Some patients will undergo some of the screening tests at home, and present results at a screening visit. This will enable them to move to the week 0 visit simultaneously and begin treatment.

At Visit 1, which will be treatment initiation, eligible subjects will be instructed on the use and side effects of subcutaneous abatacept. Patients will be started on the study drug (abatacept) 125 mg SQ weekly for subjects with body weight \geq 50KG and 87.5 mg SQ for subjects with weight <50 KG. For patients not improving with therapy by at least 5% on

at least 3 of 6 core set measures (IMACS or PRINTO measures) at week 12, they would be offered the opportunity to increase their dose of treatment to abatacept 212.5 mg SQ weekly (125 mg prefilled syringe plus 87.5 mg prefilled syringe) for subjects with weight \geq 50KG and 137.5 mg SQ weekly (87.5 mg prefilled syringe plus 50 mg prefilled syringe) for subjects with weight <50KG, or to continue on their present dose.

At each study visit, patients will undergo assessment and questionnaires to include the core set myositis activity measures (both IMACS and PRINTO core set measures), patient questionnaires (including patient/parent global activity, [Childhood] Health Assessment Questionnaire (**[C]HAQ**), Health Related Quality of Life Questionnaire (Childhood Health Questionnaire (**CHQ-PF50**) for children or **SF-36** for adults) and **PROMIS** and **PedsQL** fatigue questionnaires; at Visit 1 (week 0) and Visit 5 (week 24), the **Myositis Damage Index**- performed by a pediatric or adult rheumatologist; at visit 1 (week 0) and visit 5 (week 24); **Cutaneous Dermatomyositis Activity and Severity Index** and **Dermatology Life Quality Index**, by our affiliated dermatologist [name] or [name] on interim visits. (The dermatologic assessments will be optional) (Section 14). An open label extension of 6 months will be offered to subjects who met the primary study endpoint and are rated by the study physician as at least minimally improved from baseline visit. During this period, patients will be evaluated twice a year.

3.1 ENDPOINTS

Primary

The *primary endpoint* of this trial is to establish safety and efficacy of Abatacept in patients with refractory Juvenile Dermatomyositis

- a) Safety: Abatacept will be well-tolerated and safe.
- b) Improvement in myositis disease activity: the published IMACS myositis definition of improvement will be achieved in at least 6 of 10 patients at the end of the trial (38).

Secondary

- a) To evaluate the response rate to Abatacept in JDM using the PRINTO definition of improvement, including criteria for minimal, moderate and major clinical response (40, 41).
- b) To evaluate the response rate to Abatacept using newly developed criteria for myositis clinical response, which are pending ACR-EULAR approval (Appendix D2), as well as other top performing criteria considered at the International Myositis Response Criteria Consensus Conference.
- c) To examine response to treatment in individual core set measures of disease activity as developed by IMACS, including physician and patient/parent global activity, muscle strength (by manual muscle testing), physical function (by HAQ/CHAQ), muscle enzymes, and extra-muscular activity (by the Myositis Disease Activity Assessment Tool)

- d) To examine other core set activity measures as developed by PRINTO, including the Childhood Myositis Assessment Scale, the Disease Activity Score and CHQ-PF50
- e) Steroid-sparing benefit: 20% reduction of the corticosteroid therapy will be achieved in 6 of 10 patients at the end of the trial
- f) To examine improvement in patient reported outcomes, including health-related quality of life and fatigue measures, including the PROMIS and PedsQL fatigue questionnaires. Both patient and parent questionnaires will be obtained, for patients < 18 years of age.
- g) To examine improvement in cutaneous activity, using the Cutaneous Dermatomyositis Area and Severity Index (CDASI) and the Dermatology Life Quality Index, as well as periungual nail fold capillary density. To document changes in cutaneous findings by standardized photography.
- h) To examine improvement in muscle inflammation by examining a thigh/pelvis STIR MRI at baseline and 6 month follow-up. MRI readings will be blinded to the clinical assessment information, including, if possible, date of assessment, and study drug dose.
- i) To examine that disease damage does not increase while under treatment with abatacept, by examining the Myositis Damage Index at baseline and 6 month follow-up.
- h) To examine at baseline, 3 and 6 months biomarkers of disease including:
 - i. Immunophenotyping for CD4, CXCR3, IFN γ (TH1), CD4, CCR4, CRTH2, IL4 (TH2), CD4, CCR6, IL17a (TH17), CD4, CD25, Foxp3 (T regulatory cells), B cell markers and macrophage markers along with B71, B72, CTLA4, CT28 on fresh lymphocytes
 - ii. Isolation of T cells, B cells, dendritic cells, monocyte and macrophages, and freeze the isolated cells for subsequent molecular and functional analysis, including gene expression profiling
 - iii. Cytokine 30-plex panel on serum samples
 - iv. Peripheral blood mononuclear cells for RNA gene expression using a gene bead chip panel.

Biomarker studies will be blinded to the clinical assessment information and drug dose.

To evaluate immunogenicity and the pharmacokinetics of SC abatacept by the steady-state trough concentrations of abatacept at week 0, week 12 and week 24

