Antibodies directed against the entire Abatacept molecule or to the CTLA-4 portion of Abatacept were assessed by ELISA assays in patients with juvenile idiopathic arthritis following repeated treatment with Abatacept throughout the open-label period. For patients who were withdrawn from therapy for up to 6 months during the double-blind period, the rate of antibody formation to the CTLA-4 portion of the molecule was 41% (22/54), while for those who remained on therapy the rate was 13% (7/54). Twenty of these patients had samples that could be tested for antibodies with neutralizing activity; of these, 8 (40%) patients were shown to possess neutralizing antibodies. The presence of antibodies was generally transient and titers were low. The presence of antibodies was not associated with adverse events, changes in efficacy, or an effect on serum concentrations of Abatacept. For patients who were withdrawn from Abatacept during the double-blind period for up to 6 months, no serious acute infusion-related events were observed upon re-initiation of Abatacept therapy.

Laboratory monitoring: Complete blood counts (CBC) and platelet counts will be obtained at regular intervals during the study Blood Drawing: Subjects may experience pain, bruising and/or bleeding at the site of the needle insertion for blood drawing. Very rarely an infection may occur at the site. Subjects may also experience dizziness and/or fainting.

Hepatitis B and C and HIV blood testing: The hepatitis testing requires the drawing of blood. Being tested for hepatitis may cause anxiety regardless of the test results. If a subject has a positive test results, they may have trouble obtaining insurance or employment. There is always the possibility the test result is wrong and therefore a repeat test would be done.

Magnetic resonance imaging (MRI): MRI involves no x-rays and there are no known risks from the test, although some people may feel claustrophobic about being in a small space. No contrast agent will be administered for the MRI examination.

Photography: Photographs of skin rashes and the periungual capillaries (Optional) are taken throughout the study. The possibility exists that patients may be identifiable in some of the photographs when unique birthmarks or other identifiable skin changes are present.

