2.1 PRIMARY OBJECTIVE

AIM: To assess the safety and efficacy of subcutaneous abatacept in an open-label trial of refractory JDM in 10 adults and children.

- **Hypothesis A: *Abatacept will be well-tolerated and safe in treatment–refractory JDM patients.*** For this, the NCI Common Terminology criteria version 4.0 June 2010 will be applied. Medical records will be reviewed for the 6 months prior to enrollment to obtain adverse events prior to beginning abatacept, which will be compared to any adverse events that develop after abatacept was initiated. Particular attention will be given to serious adverse events and infections. Patient evaluations will include: vital sign measurement, physical examination, and laboratory parameters for hematology and routine chemistries.
- **Hypothesis B: *Patients will clinically improve after treatment with abatacept.*** We hypothesize that at least 6 of 10 patients will meet the myositis preliminary definition of improvement after receiving 24 weeks of therapy with abatacept.

Definitions of improvement (DOIs) for clinical trials in IIM have recently been proposed by the IMACS Group (International Myositis Assessment and Clinical Studies) for adult and pediatric myositis utilizing six core set measures among five domains of myositis disease activity (38) (**see Appendix C**). They are:

- a) Physician global disease activity;
- b) Parent/patient global disease activity;
- c) Muscle strength, utilizing manual muscle strength testing (MMT8);
- d) Physical function assessment using the (Childhood) Health Assessment Questionnaire (CHAQ);
- e) Laboratory assessment using the most abnormal serum muscle enzyme level; and
- f) Extra-muscular disease activity using the Myositis Disease Activity Assessment Tool (MDAAT). (see section 14.0: assessment tools: description) (39)

For this clinical trial, the primary endpoint will be the published Definition of Improvement (DOI): 3 of any of the 6 core set measures improved by $\geq 20\%$, with no more than 2 of the core set measures worsening by $\geq 25\%$ (worsening measures cannot include the muscle strength). (Appendix D1) (38)

The PRINTO Group (Pediatric Rheumatology International Trials Organization) has developed and validated a core set of outcome variables for the evaluation of response to therapy in JDM. (40) (Appendix C)

The additional PRINTO core set activity measures are:

- 1) Childhood Myositis Assessment Scale is used as a measure of strength;

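### MRI is the only imaging outcome with a planned blinded reading, but the scan date is masked only where possible, and the date alone shows which scan is on treatment

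*Combined protocol and SAP*

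**What the plan says.** Section 3.0 describes the trial: "This study will employ an open label nonrandomized design in the treatment of subjects with JDM". Section 4.0 sets the number of subjects at 10.

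Section 3.1 makes MRI secondary endpoint (h): "To examine improvement in muscle inflammation by examining a thigh/pelvis STIR MRI at baseline and 6 month follow-up". The blinding rule follows directly: "MRI readings will be blinded to the clinical assessment information, including, if possible, date of assessment, and study drug dose". The scans are scheduled at Visit 1 (week 0) and Visit 5 (week 24) in Section 7.1 and in Appendix E, Table 1.

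MRI also appears in Sections 2.2 and 15.0, but no other mention adds a blinding rule. The documents do not describe removal of dates from the images, the reading order, the reader, the MRI score, or what happens when date masking fails.

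Section 15.0 says that tests are unlikely to have power with so few subjects. It therefore plans to look at further measures as well, and names MRI among them. Changes from baseline to week 24 are to be tested with Student t and Wilcoxon matched-pair tests, with p<0.05 as the threshold.

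**The concern.** In a controlled trial, a reader who knows the scan order may still not know the treatment. Here order and treatment are the same thing: the first scan is untreated and the second is on abatacept, for every patient. The date is therefore the item that most needs masking, and it is the item to which the best-efforts qualifier is attached. The sentence also leaves open whether the qualifier extends to drug dose.

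Most of the evidence behind the primary endpoint is scored by people who know that the patient is being treated. In Section 2.1, five of the six core set measures (physician global, patient or parent global, manual muscle testing, the CHAQ/HAQ and the extra-muscular assessment) are rated by clinicians, patients or parents. A reading of muscle inflammation by someone who does not know the order would be useful support beside those scores. If the order is visible, an expectation of improvement can enter that reading too, and the support is weaker.

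**Working it through.** **Text check.**

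1. *Does the date identify the treated scan?* Two scans per patient, at week 0 and week 24; all patients treated; no control arm. Yes.
2. *Do the other masked items cover for the date?* Clinical assessment information tells the reader how the patient did. Dose tells the reader which regimen was used. Hiding both still leaves the order visible. No.
3. *Is a stricter rule given elsewhere?* Sections 2.2, 7.1 (Visits 1 and 5), 15.0 and Appendix E, Table 1 mention MRI without any reading rule. No.
4. *Does MRI feed the primary endpoint?* Section 2.1 says "the primary endpoint will be the published Definition of Improvement (DOI): 3 of any of the 6 core set measures improved by" a set percentage, and lists the six measures. MRI is not among them. No.
5. *Is MRI the only outcome protected from rater expectation?* No. Section 3.1 also states: "Biomarker studies will be blinded to the clinical assessment information and drug dose". The muscle enzyme in the DOI is a laboratory assay result. Photographs are collected (Section 3.1: "To document changes in cutaneous findings by standardized photography"; the photography paragraph in Section 1.3: "Photographs of skin rashes and the periungual capillaries (Optional) are taken throughout the study") and could be read blind, but no blinded reading of them is planned. MRI is thus the only *imaging* outcome with a planned blinded reading.

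**Illustration of size.** The plan gives no MRI effect size, SD or power, so there is no figure of its own to reproduce. Inputs:

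- n = 10 (Section 4.0), all pairs assumed complete.
- Threshold 0.05 (Section 15.0). Two-sided is assumed, because the plan does not say.
- Paired t-test, one of the two tests named in Section 15.0.
- True change = 0. Paired differences assumed normal.
- Reader bias b, in units of the SD of the paired difference: **assumed**, 0.1 to 0.5.

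The test statistic follows a noncentral t distribution with 9 degrees of freedom and noncentrality b × √10. The critical value is 2.262. The rejection probability is P(|T| > 2.262).

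| Assumed bias b (SD of paired difference) | Noncentrality b × √10 | Chance of p<0.05 with no true change |
|---|---|---|
| 0 | 0 | 5.0% |
| 0.1 | 0.316 | 5.9% |
| 0.2 | 0.632 | 8.8% |
| 0.3 | 0.949 | 13.6% |
| 0.5 | 1.581 | 29.3% |

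A simulation of the other planned test (exact two-sided Wilcoxon signed-rank, n = 10, 20,000 runs) gives 4.6% with no bias, 10.2% at 0.25 SD and 28.6% at 0.5 SD. The choice of test makes little difference.

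**The case against.** The strongest reply is that the plan already blinds the reader to clinical information and means to hide the date where it can. The qualifier does not say that dates will be shown. MRI is one of many secondary endpoints and cannot change the 6-of-10 result. The plan itself expects little from significance tests, and nowhere names MRI as the check on the clinical scores. The bias range is assumed, no MRI score is defined from which to calibrate it, and at 0.1 to 0.2 SD the error rate of 6% to 9% stays close to nominal.

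Most of this stands, and it limits the weight of the point. It does not remove it. A best-efforts clause allows a reading with the order visible, and nothing requires such a reading to be identified or reported.

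A reader might infer that MRI is the one efficacy outcome in this trial that could be read fully blind. The documents do not support that: biomarkers are blinded to clinical data and dose, the DOI enzyme comes from an assay, and photographs could be read blind. (The biomarker sentence does not mention sample date, and those markers do not image muscle inflammation.) A reader might also infer that an order-unmasked MRI would corroborate nothing. That goes too far as well: possible expectation bias weakens the evidence without voiding it, and blinding to clinical response would remain.

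**Conclusion.** The point holds in a limited form. As written, the plan allows the MRI reader to know which scan is on treatment, in a design where that knowledge is the main route for expectation bias. It concerns a secondary outcome that Section 15.0 uses as supportive evidence. It does not touch the primary DOI result.

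The size cannot be established from the documents. Under the assumptions above (no true change, 10 complete pairs, normal differences, two-sided 0.05), an assumed shift of 0.1 to 0.5 SD of the paired difference moves the false-positive chance from 5% to about 6% to 29%. That range shows direction and scale only. It does not estimate how much bias would occur.

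The change is worth making because it is cheap and because order masking, once lost, can be recovered only by re-reading the scans.

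**What to change.** In Section 3.1, endpoint (h), delete the qualifier so that masking of both scan date and drug dose is required. This also settles whether dose is covered. Then add that:

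- dates and identifiers are stripped from both scans of each patient;
- the same reader scores both scans of a coded pair, presented in random order;
- readings are done in batches of complete pairs;
- scores are locked before the order is revealed;
- any reading where masking failed is reported.

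The MRI score itself should be named in the same place, since none is defined.

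**Cost.** At most 2 × 10 = 20 scans need to be de-identified and coded. No extra visit, scan or reader is needed. The documents do not describe how scans are handled, so the exact staff time is unknown, but it should be small. The one real downside is that MRI scores become available somewhat later. Batching keeps this modest. Waiting for the last week-24 scan would be slow: at the synopsis maximum of 1 patient per month, the tenth patient enters about 9 months after the first and is scanned about 5.5 months later, roughly 14.5 months after the first baseline scan.

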3.2 SAFETY ENDPOINTS

Safety assessment will include adverse events, vital signs, physical examination findings, laboratory parameters and NCI common terminology safety assessment, including focus on serious adverse events and the infection module. This will be collected in person during study visits, but in between study visits, a phone call will be made at weeks 2, 4,8,10,14,16, 20 and 22 to review adverse events.

Patient evaluations include:

1. Vital sign measurement, physical examination

2. Laboratory parameters for hematology, routine chemistry, muscle enzymes and urinalysis
3. NCI Common Toxicity assessment (version 4.0 June 2010) including focus on serious adverse events and the infection module.
4. Adverse event monitoring
5. Assessment of primary and secondary efficacy endpoints

4.0 SUBJECT POPULATION

Enrolled patients will include male and female, adults with a definite or probable diagnosis of JDM and pediatric patients \geq seven years of age and older with definite or probable JDM (using the criteria of Bohan and Peter-Appendix A) [33] with greater than four months of disease duration. Patient body weight will be at least 25 kg. Patient enrolment will occur at the GWU Myositis Center of the Medical Faculty Associates. The total number of subjects will be 10. A diagnosis of DM prior to age 18 is considered JDM; patients with JDM enrolled after age 18 will continue to be classified as JDM.

A log will be kept of all patients screened for study enrollment and will document the reasons for exclusion for each subject not entered. Every effort will be made to keep patients in the study until they complete all study procedures. We plan to screen up to 30 patients in clinic to enroll 10 patients. Additional patients may be screened by phone and not seen in clinic if not qualified for the protocol.

4.1 Inclusion Criteria:

In order to qualify for participation, a subject must meet all of the following criteria:

1	Considering 1A-1F below, does the subject have documented criteria for probable (2 + rash) or definite (3-4 + rash) juvenile DM by the criteria of Bohan and Peter?
	
 a. Does the subject have documented symmetric proximal muscle weakness on exam? b. Does the subject have documented Gottron's papules or Heliotrope rash on exam? c. Does the subject have documented elevations of any of the following muscle enzymes (CK, LD, AST, ALT or aldolase)? d. Was the age at diagnosis < 18 years? e. Has the subject had an EMG and if so, if so, does the subject have documented EMG evidence for myopathy f. Does the subject have documented muscle biopsy evidence of dermatomyositis?
2	Is the body weight at least 25 kg or over?
3	Is the subject at least 7 years or older?
4	Does the patient reside within the United States or Canada?
5	Considering 5A-5J below, Does the patient have refractory myositis? (As defined by the intolerance to or an inadequate response to corticosteroids plus at least one other IS agent?)
	a. Has the patient had intolerance or an inadequate response to prednisone for at least one month?
	b. Has the patient had intolerance at any time, or an inadequate response for at least 3 months to azathioprine at least 2 mg/kg/d or 150 mg/day?
	c. Has the patient had intolerance or an inadequate response to methotrexate at least 15 mg/week or 0.3 mg/kg or 15 mg/m ² / week for at least 3 months?
	d. Has the patient had intolerance or an inadequate response to mycophenolate mofetil at least 30 mg/kg/d or 1000 mg bid for at least 3 months?
	e. Has the patient had intolerance or an inadequate response to cyclophosphamide at least 1.0 mg/kg/d poor 500 mg/m ² /month IV for at least 3 months?
	f. Has the patient had intolerance or an inadequate response to oral tacrolimus for at least 3 months?
	g. Has the patient had intolerance or an inadequate response to cyclosporine at least 2.5 mg/kg/d for at least 3 months?
	h. Has the patient had intolerance or an inadequate response to IVIG at least 1.0 g/kg/month for at least 3 months?

	i. Has the patient had intolerance or an inadequate response to an anti-TNF agent (including Etanercept, Infliximab, Humira, etc) for at least 3 months?
	j. Has the patient had intolerance or an inadequate response to 2 infusions of Rituximab (375mg/m ² (for 4 doses), or 500 mg/m ² or 1000 mg for 2 doses)?
6	Considering 6a-6f, Does the patient have a moderately active disease (MD global VAS with a minimum value of 2,5 cm on a 10 cm scale plus another 2 other abnormal Core set Measures as listed above (7b-7f)
	a. Does the MD global VAS have a minimum value of 2.5 cm on a 10 cm scale
	b. Is the MMT-8 score no greater than 125/150
	c. Does the Patient/parent Global VAS have a minimum value of 2.0 cm on a 10 cm scale
	d. Does the CHAQ/HAQ disability index have minimum value of 0.25
	e. Is at least one of the muscles enzymes (including CK, aldolase, LDH, AST and ALT) elevated at a minimum level of 1.3 times the upper limit of normal. If more than one muscle enzyme is identified as being elevated and meeting the above guidelines, then the most abnormal will be selected and this enzyme will be the target enzyme followed to evaluate disease improvement or worsening.
	f. Does the Global extra-muscular disease have a score with a minimum value of 2 cm on a 10 cm VAS scale.
7	Is the prednisone dose stable for 4 weeks prior to the screening visit? (recommended dose ≤ 1.0 mg/kg/day)
8	Background therapy with at least 1 non-corticosteroid immunosuppressive agent is required at a stable dose (timeframe mentioned below) prior to the screening visit with the following exception: 
 • There is written documentation in the medical record that the patient is intolerant of an IS agent which is defined as side effects that require discontinuation of the medication(s) or an underlying condition that precludes the further use of the IS medication. Stable dose for 4 weeks: Prednisone, IVIG, IV Methylprednisolone Stable dose for 6 weeks: Methotrexate, Azathioprine, mycophenolate mofetil, leflunomide, cyclophosphamide, tacrolimus or cyclosporine
9	Did an immunosuppressive agent, discontinued prior to the screening visit, have the required washout period: 
 • 4 weeks for prednisone, IV methylprednisolone and methotrexate • 8 weeks for other IS agents including IVIG, Azathioprine, mycophenolate, mofetil, leflunomide, cyclophosphamide, tacrolimus or cyclosporine. • For discontinuation of biologic therapies-with the required washout period

Ve

	Half-life	Waiting period before enrollment (5 half-lives)	Washout Period
Etanercept	70 hours	15 days	1 month
Adalimumab	14 days	70 days	2 months

	washout period for Rituximab is 3 month+ and CD19 has to be detectable and IgG level is within normal limits (normal serum levels of IgG per reference lab: 7-9 years ≥ 572 mg/dl, 10-11 yrs ≥ 698 mg/dl, 12-13 yrs ≥ 759 mg/dl, 14-15 yrs ≥ 716 mg/dl, 16-19 yrs ≥ 549 mg/dl, >19 yrs ≥ 700 mg/dl).
10	If on hydroxychloroquine or colchicine, the dose should be stable for 6 weeks prior to Visit 1
11	Is the statin or fibric acid derivative drug dose stable for 6 weeks prior to the screening visit?
12	Ability of patient or parent to complete self-report questionnaires.
13	If of reproductive potential**, does the patient agree to use a reliable method of birth control during the 24 week duration of the trial and for 100 days after the last dose of study drug was administrated?
14	Does patient agree to forgo immunization with a live vaccine during the course of the study and for at least 3 months after discontinuation of study drug?
15	Patients must have a letter from the referring rheumatologist or specialist supervising the care of the JDM, agreeing to the patient's participation in the study and to continuing to provide care for the patient, including emergency care during the trial.
16	Has the patient or parent provided informed consent, and assent when applicable for patients ages 8-17 or younger, for participation in study?
17	For children of divorced or separated parents: A copy of the parental custody papers will be received. One parent has sole custody and will sign the consent, OR There is joint custody and 1 parent gives permission for the other parent to sign consent/be in charge of medical decisions, OR Both parents sign the consent

****Age and Reproductive Status Reproductive Status: Definition of Women of Child-Bearing Potential (WOCBP).** WOCBP comprises women who have experienced menarche and who have not undergone successful surgical sterilization (hysterectomy, bilateral tubal ligation, or bilateral oophorectomy) or who are not post-menopausal.

The following women are WOCBP:

- Women using the following methods to prevent pregnancy: Oral contraceptives, other hormonal contraceptives (vaginal products, skin patches, or implanted or injectable products), or mechanical products such as intrauterine devices or barrier methods (diaphragm, condoms, spermicides).
- Women who are practicing abstinence.
- Women who have a partner who is sterile (e.g., due to vasectomy).

WOCBP must be using an acceptable method of contraception to avoid pregnancy throughout the study and for up to 10 weeks after the last dose of study drug in such a manner that the risk of pregnancy is minimized.

WOCBP must have a negative urine pregnancy test result (minimum sensitivity 25 IU/L or equivalent units of HCG) within 0 to 48 hours before the first dose of study drug.

Women must not be breast-feeding.

Sexually active fertile men must use effective birth control if their partners are WOCBP.

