Evaluation of Risk/Benefit Ratio: If abatacept proves to be effective, many such patients with JDM may ultimately benefit from this therapy. Such benefits may include improved symptoms and health. Practitioners may gain increased knowledge and treatment of myositis in clinical practice. Subjects participating in this study may experience some benefit during the period of study medication therapy. Evaluation is performed as per the statistical information provided in the protocol. The risks for those subjects involved in this study are reasonable when compared to the potential

disease damage and catastrophic sequelae that occurs in adult and pediatric patients with inflammatory myopathy.

Reproductive Risks: Animal studies to determine the effects of the study drug on the fetus have not been done. To avoid risk to the fetus, it is important that female participants or female partners of male participants take care to avoid becoming pregnant during this study. Avoiding sexual activity is the only certain method to prevent pregnancy. However, females of child-bearing potential must be willing to use an appropriate method of birth control (such as female use of a diaphragm, intrauterine device (IUD), or contraceptive sponge, in addition to male use of a condom) or the female should be using prescribed “birth control” pills, injections, or implants throughout the study. Even with use of these birth control measures, pregnancy could still result. The risks of receiving the study drug while pregnant include potential loss of pregnancy or possible birth defects. Females of child-bearing potential will undergo a urine pregnancy test prior to exposure to the study drug. In the pediatric group the parent signing the consent will be informed of the result of the pregnancy test.

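### For women of child-bearing potential, inclusion 13 requires contraception for 100 days after the last dose, but the note explaining that criterion says up to 10 weeks

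*Combined protocol and SAP*

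**What the plan says.** Three places in the protocol deal with contraception.

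- **Section 4.1, inclusion criterion 13.** Patients of reproductive potential must agree to a reliable method "during the 24 week duration of the trial and for 100 days after the last dose of study drug". The criterion makes no distinction by sex. It carries a double asterisk.
- **The double-asterisk note after the inclusion table (Age and Reproductive Status).** It defines women of child-bearing potential (WOCBP) and requires contraception of them during the whole study and "for up to 10 weeks after the last dose of study drug". A separate sentence asks sexually active fertile men with WOCBP partners to use effective birth control. It gives no duration.
- **Section 1.3.2, Reproductive Risks.** Women are told to use birth control, for example "injections, or implants throughout the study". The paragraph states no period after the last dose.

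Section 7.1 (Visit 5 and the extension visit) and Appendix E Table 1 allow dosing beyond week 24, in an extension of up to 6 months shown as weeks 25 to 48.

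**The concern.** Inclusion 13 and its note govern the same women and count from the same event, the last dose, but give different durations. The note is where site staff would look to apply the criterion, so the two figures meet at the point of use.

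The instruction exists for fetal safety. Section 1.3.2 says that animal studies of fetal effects have not been done, and it names pregnancy loss and birth defects as possible consequences of exposure in pregnancy.

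Little in the schedule would catch a misapplied period:

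- Under Section 7.1, patients who decline the extension receive their last injection at week 24, leave the study and return to their local rheumatologist. Extension patients are dosed at the visit at which they leave.
- Appendix E Table 1 shows no visit or pregnancy test after the final dose.
- Under Section 12.3, serious adverse events, with pregnancy handled as one, are collected for 30 days after dosing stops. Later events are to be reported only if believed related to the drug or a study procedure.

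The end of the contraception period therefore depends on what the patient was told before leaving.

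**Working it through.** No sample size, power or error rate is involved. The check is a unit conversion and a comparison of passages.

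**Step 1. The post-dose period for WOCBP.**

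- Inclusion 13: 100 days after the last dose.
- Note: up to 10 weeks, 10 × 7 = 70 days.
- Difference: 100 − 70 = 30 days. Because the note says up to, 70 days is its maximum, so the gap is at least 30 days.
- With a last dose at the nominal week 24 (24 × 7 = day 168), inclusion 13 runs to day 168 + 100 = 268, and the note to day 168 + 70 = 238 at the latest.

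**Step 2. Which behaviour breaches which passage.**

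| Contraception stops after the last dose at | Inclusion 13 (100 days) | Note (up to 10 weeks) |
|---|---|---|
| 70 days | breached | met |
| 100 days | met | met |

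Only the shorter reading produces a breach.

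**Step 3. Fertile men.** Inclusion 13, read without regard to sex, gives them 100 days. The note tells them to use birth control but gives no duration. For men this is a missing figure in the note, not two figures in conflict.

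**Step 4. The extension.** Both passages count the post-dose period from the last dose, so for an extension patient it starts at the last extension dose. The time on drug before that dose is treated differently:

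- Inclusion 13 names the 24-week trial, which ends at nominal day 168.
- The last extension week in Appendix E Table 1 is week 48, 48 × 7 = day 336.
- Read literally, inclusion 13 does not name the dosing time from day 168 to day 336, up to 336 − 168 = 168 days.
- For WOCBP the note fills this if its reference to the whole study includes the extension. For men the note states no period.

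**Step 5. Reproductive Risks.** Section 1.3.2 covers the study period and neither sets nor denies a period after it. It is silent on the point and does not contradict the other two passages.

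**The case against.** The strongest reply is that the enrolment rule already settles the matter. Section 4.1 requires every inclusion criterion to be met, so each enrolled patient of reproductive potential has agreed to 100 days, and the note's ceiling does not cancel that agreement. Following the longer period satisfies both passages. The protocol also schedules urine pregnancy tests at the treatment visits and the extension visit, and it requires pregnancies to be reported. Only 10 patients are planned.

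Most of this stands as a limit on the point. It does not remove the contradiction, because the protocol never says that the longer period prevails and the on-treatment tests do not reach the weeks after the last dose.

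A reader might draw four stronger conclusions, which the documents do not support:

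- **That following either figure breaches the other passage.** Only stopping at 10 weeks does.
- **That the 30-day conflict affects every patient of reproductive potential.** The 10-week figure is addressed to WOCBP only.
- **That Section 1.3.2 is a third, conflicting rule, or that the consent form is inconsistent.** The first is silence, and the consent pages were not available for this review.
- **That extension patients have no post-dose rule.** Both passages already count from the last dose.

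Nor do the documents show what exposure remains between days 70 and 100, so the clinical weight of those 30 days cannot be judged from them.

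**Conclusion.** The point holds for WOCBP: two current, mandatory passages, one of them the note to the other, differ by at least 30 days on how long contraception must continue. A woman who follows the note alone ends contraception at least 30 days before inclusion 13 allows. The lesser gaps are the missing duration for fertile men in the note and the restriction of inclusion 13 to the 24-week trial.

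This rests on reading the double asterisk as linking the criterion to the note and on taking a week as seven days. It takes no view on which period is correct. The number of women affected cannot be known in advance. The efficacy analysis is untouched. Because this is a stated safety rule that cannot be applied in two ways, it should be corrected.

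**What to change.** The sponsor should reconcile the passages to a single post-dose period of its own choosing, and then:

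1. State that period in identical words in inclusion 13 and in the double-asterisk note, for women and for men, without the words up to.
2. Reword inclusion 13 so that it covers all time on study drug, including the extension, followed by the post-dose period.
3. Add the same period to the Reproductive Risks paragraph in Section 1.3.2.
4. Check that the consent and assent forms carry the same period, and change them if they do not.

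The cost is wording only. No visit, test, sample size or analysis changes.
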